INVESTIGATIONAL PRODUCT	
A panitumumab-IRDye800 dose of 50 mg, will be systemically infused 1 to 5 days before surgery. Panitumumab-IRDye800 has been manufactured under current good manufacturing practice (cGMP) by LICOR Biosciences Inc. [name] (co-PI) currently holds the IND (119474).
 
On the day before surgery 2 mCi Lymphoseek (^{99m}Tc-tilmanocept) will be administered locally around the primary tumor for sentinel node mapping. Lymphoseek is obtained in unit doses from Cardinal Health.

TREATMENT SCHEDULE	
A panitumumab-IRDye800 dose of 50 mg, will be systemically infused 1 to 5 days before surgery. On the day before surgery, to subjects undergoing sentinel node biopsy, the standard dose of ~2 mCi Lymphoseek will be administered locally around the primary tumor after which lymphoscintigraphy and SPECT/CT imaging will be performed per standard of care to determine the number and location of foci of radiopharmaceutical uptake indicating sentinel nodes.
 
On the day of surgery, intraoperative fluorescence imaging will be performed using an intraoperative optical imaging device (a list of devices is provided in Appendix B). Per standard of care, for the subjects undergoing sentinel node biopsy, a gamma probe will be used to search for radioactive lymph nodes as well. Ex vivo fluorescence imaging and gamma counting of the excised specimens will be performed prior to and after pathological assessment. At all steps, equipment will be used that does not violate or destroy the pathological tissues.

PRIMARY OBJECTIVE(S)	The primary objective of the study is to determine if near-infrared fluorescence imaging of panitumumab-IRDye800 can identify metastatic disease in regional neck lymph nodes of subjects with head and neck squamous cell carcinoma (HNSCC).
SECONDARY OBJECTIVE(S)	Determine if panitumumab-IRDye800 can identify sentinel nodes with the same accuracy as Lymphoseek.

SAMPLE SIZE AND STUDY DURATION	
It is anticipated that 20 subjects will be enrolled into the study. Each subject will be followed for 30 days following the last dose of study medication. Based on the enrollment rate from the panitumumab-IRDye800 trial in HNSCC, it is anticipated that the study will require 2 years to be completed.

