2.4.2.3. Pharmacokinetic intervals

Clearance of panitumumab occurs through the binding in the liver and through the reticuloendothelial system as occurs with endogenous immunoglobulin. Because the

pharmacokinetics of single dose panitumumab are well known and the pharmacokinetics of panitumumab and panitumumab-IRDye800 are nearly the same in non-human primate studies (see toxicology section), only limited pharmacokinetics will be performed. Blood levels of panitumumab-IRDye800 and free IRDye800 will be monitored on Day 0 before infusion and approximately 1hour after end of infusion), on Day 1 as available, on the day of surgery (Day 1 to 5 post-infusion), Day 1 to 3 post-surgery as available, Day of discharge, and Day 30 post-infusion of the study drug.

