4.8 Alternatives and Risk Protection / Mitigation

Alternatives

- This study is in the setting of tumor and LN node excision of suspected squamous cell carcinoma, and the experimental component is infusion of panitumumab-IRDye800, and Lymphoseek with planar and SPECT/CT imaging, which may help the surgeon visualize LN status and location. Additionally, using a handheld gamma counter post-injection may also help the surgeons to locate nodes with Lymphoseek uptake. Both approaches have been shown to decrease overall time in surgery. The surgery itself is considered regular medical care. Therefore, the alternative to participating in this study is to have the surgery without panitumumab-IRDye800 and/or Lymphoseek administration.

Procedures to protect against and minimize potential risks:

- This study is designed to enroll appropriate subject populations (see Section 3.1 Inclusion Criteria, and Section 3.2 Exclusion Criteria).
- Subjects will be monitored regularly for AEs by the investigators and the study team after investigational panitumumab-IRDye800 and surgery, through 30 days (\pm 7 days) post-panitumumab-IRDye800 infusion.
- Subjects will be given a 24-hour emergency number in case problems arise between clinic visits.
- Subject records will be kept in a secure location at Stanford University Medical Center accessible only to authorized personnel.

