5.2.1.5 Hypomagnesemia and Electrolyte Abnormalities

In one study, hypomagnesemia (NCI-CTC Grade 3 or 4) requiring oral or intravenous electrolyte repletion occurred in 2% of subjects. Hypomagnesemia occurred 6 weeks or longer after the initiation of panitumumab (package insert). Both hypomagnesemia and hypocalcemia occurred in some subjects. Electrolytes should be monitored periodically during treatment and for 8 weeks after the completion of therapy when used as anti-cancer treatment. For this study, electrolytes will be monitored for 30 days after administration of panitumumab-IRDye800. Replete electrolytes as necessary using standard infusion guidelines.

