7.5 Safety Monitoring and Reporting

7.5.1. Monitoring and Recording of Adverse Events

Both serious and non-serious AEs will be clearly noted in source documentation and listed on study-specific Case Report Forms (CRFs). The PD or designee will assess each AE to determine whether it is unexpected according to the Informed Consent, Protocol Document, or Investigator's Brochure, and related to the investigation.

All adverse events (AEs), regardless of seriousness or relationship to study drug, are to be collected only on designated study dates from signing of informed consent through 30 days after administration of study drug, and recorded in the study-specific worksheets, with the following exceptions:

- AEs that are solely laboratory values; are not related to the study drug; AND are clinically non-significant may not be collected.

- Non-serious AEs that occur within 30 (+/-7) days after surgical resection of the tumor; are not related to the study drug; are not clinically significant; AND are expected in the post-surgery clinical setting may not be collected.
- SAEs that occur from signing of informed consent to prior to Day 1 may not be collected unless assessed as possibly, probably or definitely related to a study procedure.

All patients enrolled in this study receive surgical intervention in the course of their standard of care. As a consequence of this surgery, patients may experience certain expected and normal adverse events. The following post-operative adverse events will be captured only in the patient's Electronic Health Record (EHR) source documentation and not in the adverse event log. If the adverse event exceeds the grading listed below or occurs outside the post-operative time window, the adverse event will be recorded in the Adverse Event Logs.

- Surgical wound site and associated, expected secondary signs and symptoms, including:
 - CTCAE v5.0 Grade 1 erythema, edema, and pruritis.
 - CTCAE v5.0 Grade 1 pain associated with surgical wound, including headaches – mild pain, little to no limit on adult daily life.
 - CTCAE v5.0 Grade 1 nausea, vomiting, and dysphagia.
 - CTCAE v5.0 Grade 1 weight loss, anemia, and electrolyte abnormalities.
 - CTCAE v.5.0 Grade 2 trismus.

Whenever possible, symptoms should be grouped as single syndrome or diagnosis. The Investigator should specify the date of onset, maximal intensity, corrective therapy given, outcome, and his/her assessment of causality.

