9. STUDY CALENDAR

9.1 Study Procedures Table

Enrolled subjects will follow schedule of evaluations provided below:

	Screening/ Pre-treatment (≤ 30 days before treatment)	Day 0	Day 0 to 4	Day of Surgery (Day 1 to 5)	Day of discharge ¹²	Day 15 (±4 days ¹²)	Day 30 (±4 days)
Informed Consent	X						
Medical History	X						
Physical Examination¹	X	X			X	X	
Vital Signs	X	X	X	X	X	X	
Height and weight	X	X					
Performance Status¹	X				X	X	
ECG	X²						
Chemistries³	X	X		X		X	
Hematology⁴	X					X	
Serum pregnancy¹¹	X	X¹¹					
PK - fluorescent-labeled antibody⁵		X	X⁵	X	X	X	
PK – Immunogenicity⁶		X				X	
IV infusion of Panitumumab-IRdye800⁷	X						
Local administration of Lymphoseek¹³			X				
Sentinel node mapping (lymphoscintigraphy + SPECT/CT imaging)¹³			X				
Surgical Resection				X⁸			
Tumor imaging				X⁹			
Pathological evaluations¹⁰				X			
Adverse events¹⁵		X	X	X		X	X
Concurrent medications¹⁴	X	X	X	X		X	X

1. A physical examination and performance status assessment will be done at screening; Day 0; Day of discharge; and Day 15. Examinations collected for surgical procedure are acceptable for screening purposes. Examinations do not have to be repeated on Day 0 if completed within 21 days of infusion.
2. ECG will be obtained at screening to evaluate baseline. A previous ECG that was obtained as part of standard of care may be used as the screening ECG as long as it was obtained within 21 days of infusion.
3. Chemistries to include a standard basic metabolic profile with magnesium and phosphorus. Chemistries and other blood work collected for surgical procedure are acceptable for screening purposes. Chemistries do not have to be repeated on Day 0 if completed within 21 days of infusion. On Day of Surgery and Day 15 only magnesium and phosphorus are collected.
4. Hematology (ie, CBC W/O DIFF) values include WBC; RBC; Hgb; hematocrit and platelet counts. Blood work collected for surgical procedure are acceptable for screening purposes.

5. Serum level of panitumumab-IRDye800 will be drawn on Day 0 prior to dose and 30 (\pm 10) minutes after the end of infusion, on Day 1 if applicable, day of surgery, up to once a day on Days 1, 2, and 3 post-operative as available, Day of discharge, and Day 15 to assess circulating fluorescent-labeled antibody and unconjugated dye.
6. Blood will be obtained pre-infusion and 15 days after infusion and banked for future immunogenicity testing. Immunogenicity testing time points will not vary with dose.

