9.2.6 Day 15 (\pm 4 days)

- Physical examination
- Vital signs (blood pressure, heart rate, respiratory rate, temperature)
- Performance Status
- Serum magnesium and phosphorus; any other blood tests as needed to assess for any ongoing abnormalities, per PIs discretion
- CBC and platelets
- Blood sample for future assessment of immunogenicity
- Blood sample for panitumumab-IRDye800 antibody pharmacokinetics
- Assessment for adverse events
- Assessment for concomitant medications

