9.2.7 Day 30 (\pm 4 days)

- Investigator or study staff will contact the subject by telephone or review of electronic medical record data to collect any additional adverse events that are attributable to the study and/or concomitant medications.

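### The last scheduled adverse event contact may fall on Day 26, up to four days before the 30-day collection period ends

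*Combined protocol and SAP*

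**What the plan says.** All references are to the combined protocol and SAP.

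**Adverse event period.** Section 7.5.1 covers serious and non-serious events, related or not, and states that they "are to be collected only on designated study dates from signing of informed consent through 30 days after administration of study drug", with listed exceptions. The synopsis makes a matching promise: "Each subject will be followed for 30 days following the last dose of study medication". Section 4.7 takes subjects off study only when the 30-day safety observation is complete.

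**Final contact.** The last column of the Section 9.1 calendar, and the heading of Section 9.2.7, is Day 30 with a tolerance of ±4 days. Section 9.2.7 describes it: "Investigator or study staff will contact the subject by telephone or review of electronic medical record data to collect any additional adverse events". The sentence then restricts these to events attributable to the study. No blood is drawn.

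**Section 4.8.** "Subjects will be monitored regularly for AEs by the investigators and the study team after investigational panitumumab-IRDye800 and surgery", up to 30 days after infusion, here with a tolerance of ±7 days.

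**Laboratory follow-up.** Section 5.2.1.5: "For this study, electrolytes will be monitored for 30 days after administration of panitumumab-IRDye800". Section 9.2.6, at Day 15 ±4, has "Serum magnesium and phosphorus; any other blood tests as needed to assess for any ongoing abnormalities, per PIs discretion". Section 2.4.2.3 ends its list of blood levels with "Day of discharge, and Day 30 post-infusion of the study drug", whereas footnote 5 of Section 9.1 ends with "Day of discharge, and Day 15 to assess circulating fluorescent-labeled antibody and unconjugated dye".

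**The concern.** When events are collected only on designated dates, the last of those dates decides how much of the stated period is covered. A tolerance of ±4 days is ordinary for a visit. Here, however, the contact closes a fixed period, and the early half of the tolerance lets it close before the period is over. A subject contacted on Day 26 has been asked about 26 days, while Section 7.5.1 and the synopsis speak of 30.

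What is at stake is the completeness of non-serious event data at the end of follow-up, and equal coverage across subjects. The wording of the contact adds to this. Section 9.2.7 asks only for events attributable to the study, but Section 7.5.1 collects events regardless of relationship.

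Sections 5.2.1.5 and 2.4.2.3 raise a separate, editorial question. They describe Day 30 laboratory work that the calendar does not contain.

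**Working it through.** The plan gives no figure for this point, so the check is date arithmetic and a comparison of sections. Infusion is Day 0, so Day 30 is 30 days after study drug.

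**Scheduled coverage**

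- Inputs: period end, Day 30 (Section 7.5.1); final contact, Day 30 ±4 (Sections 9.1 and 9.2.7).
- Earliest compliant contact: 30 − 4 = Day 26. Latest: 30 + 4 = Day 34.
- Gap at the earliest contact: 30 − 26 = 4 days (Days 27 to 30), and 4/30 = 13% of the period.
- Scheduled coverage = the smaller of the contact day and 30. A contact on Day 26 gives 26 days. A contact on any of Days 30 to 34 gives 30 days, because collection stops at Day 30. The range is 26 to 30 days.

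**Dose-limiting toxicity**

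- Section 4.4 counts 15 days from treatment with either agent.
- Lymphoseek is given the day before surgery, and surgery is on Day 1 to 5, so Lymphoseek falls on Day 0 to 4.
- The latest end of the 15 days is 4 + 15 = Day 19, which is before Day 26. The gap does not touch this assessment.

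**Analyses.** The primary and secondary analyses in Section 12.1 compare imaging of lymph nodes with histopathology. They use no adverse event data.

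**Window after the change**

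- Now: Day 26 to 34, which is 9 days.
- With Day 30 (+4): Day 30 to 34, which is 5 days. The gap is 30 − 30 = 0.

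**Laboratory sections against the calendar**

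- Electrolytes: 30 days in Section 5.2.1.5. The last scheduled draw is Day 15 ±4, that is Day 11 to 19, so it falls 30 − 19 = 11 to 30 − 11 = 19 days before Day 30. Footnote 12 allows further blood as needed to follow up abnormal values.
- Last blood level: Day 30 in Section 2.4.2.3, Day 15 in footnote 5.
- First blood level after infusion: about 1 hour in Section 2.4.2.3, but 30 ± 10 minutes (20 to 40 minutes) in footnote 5 and Section 9.2.2.

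**The case against.** The strongest reply is that little can be lost. A Day 26 contact does not end participation: under Section 4.7 the subject stays on study until the 30 days are complete. Section 7.5.2 has subjects instructed to report new or worsening symptoms throughout, with such reports entered in the CRF, and serious events go to the sponsor within 24 hours of knowledge. Section 4.8 provides a 24-hour number. Section 7.5.1 already excuses non-serious post-surgical events that are unrelated, expected and not clinically significant. The agent is a single dose with an expected half-life of about 2.3 days or less (Section 4.2), so Day 26 is at least 26/2.3 = 11 half-lives after infusion.

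All of this stands, and it is why the point is minor. None of it adds a scheduled date. A non-serious event that starts in Days 27 to 30 and is not volunteered can still be missed.

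Several stronger readings are tempting but are not supported:

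- *Follow-up varies from 26 to 34 days.* It does not, because Section 7.5.1 stops collection at Day 30 even if the call is made on Day 34.
- *Section 4.8 allows a final contact on Day 23.* Its ±7 days belongs to a general monitoring statement. The scheduled contact is set in Section 9.
- *The shortfall in Cohort 1 is up to 8 days, counted from Lymphoseek.* This assumes that Lymphoseek starts the 30-day clock. The synopsis wording could be read so, and Section 5.1 describes both agents as study drug. But Section 4.8 counts the 30 days from the panitumumab-IRDye800 infusion, as does the calendar, and Section 2.4.2.2 sees no need for additional safety measures for Lymphoseek.
- *Staff cannot tell whether a Day 30 blood sample is due.* Section 2.4.2.2 refers to Section 9 for the safety measurements, and Section 9.1 says that subjects follow its schedule. The operative schedule is clear, and Sections 5.2.1.5 and 2.4.2.3 simply do not match it.

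**Conclusion.** The point holds and is minor. The calendar permits a final contact up to 4 days before the stated period ends, so at most 4 of 30 days (13%) lack scheduled collection, and scheduled coverage runs from 26 to 30 days between subjects. These are worst-case figures counted from the infusion. The documents do not say how often contacts are made early, and a contact on Day 30 or later has no gap.

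A reader might infer that events in Days 27 to 30 go unrecorded. The documents do not support that: volunteered symptoms and known serious events are still captured. Only non-serious events that the subject does not volunteer are exposed. The dose-limiting toxicity assessment and the primary and secondary analyses are unaffected.

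The mismatches in Sections 5.2.1.5 and 2.4.2.3 are real but editorial, since Section 9 governs what is done.

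**What to change.** 1. In Sections 9.1 and 9.2.7, change the final contact to Day 30 (+4 days).
2. In Section 9.2.7, ask about all adverse events that Section 7.5.1 requires, through Day 30, instead of only those attributable to the study.
3. In Section 4.8, use the same tolerance.
4. As an editorial clean-up, bring Section 5.2.1.5 (electrolytes) and Section 2.4.2.3 (last blood level and first post-infusion time) into line with the Section 9 calendar, with a reference to the as-needed blood tests in footnote 12.

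The Day 15 ±4 visit can stay as it is.

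The cost is a wording amendment and the loss of four early scheduling days (Days 26 to 29), so the contact window goes from 9 days to 5. No visit or blood draw is added, and the latest contact remains Day 34. Item 4 gives up a written statement of 30-day electrolyte monitoring that the calendar does not deliver. If the sponsor does want a Day 30 value, a draw would have to be added to Section 9.

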7.5.2. Reporting Adverse Events and Serious Adverse Events

Non-serious adverse events will be reported annually to FDA via an Annual Report (IND 119474) and to IRB via Continuing Review.

The PD (aka Principle Investigator) must immediately report within 24 hours of knowledge of event to the Sponsor (ie, IND Holder, [name]), any serious adverse event, whether or not considered related to study drug. SAEs of all grades will be reported to the Sponsor using the Stanford Cancer Institute SAE CRF. The investigator must provide a detailed description of the event, the treatment regimen, relevant laboratory and evaluations and assessment of the relationship of the AE to the study drug. All relevant information should be reported as it becomes available.

SAEs CTCAE Grade 3 and above, and all subsequent follow-up reports will be reported to the Stanford Cancer Institute Data and Safety Monitoring Committee (DSMC) using the study specific CRF regardless of the event's relatedness to the investigation. Following review by the DSMC, events meeting the IRB definition of an "Unanticipated Problem" (UP) will be reported

to the IRB using eProtocol within 10 working days of DSMC review, or within 5 working days for deaths or life-threatening experiences.

Adverse events deemed serious, unexpected (ie, not described in the protocol, Investigator's Brochure or informed consent documents) and related to study drug must be reported to Sponsor using the FDA MedWatch form 3500a within 24 hours of knowledge of event. The Sponsor is responsible for deciding whether the event meets IND Safety Reporting criteria.

Events will be submitted to Sponsor [name], at:

[name]
Professor of Otolaryngology-Head and Neck Surgery & Radiology		
[name]
[name]
[name]
[contact]		94305

It will be the responsibility of the Sponsor to provide to the FDA all information concerning significant hazards, contraindications, side effects or precautions felt significant to the safety of the drug being studied. The PD is responsible for accurate and timely communication to the Sponsor of any events reportable to FDA. Subjects will be instructed prior to participation on the importance of reporting any symptoms (new or worsening), and/or any physical changes throughout their participation in the study. These events will be recorded accordingly in the CRF. Abnormal laboratory and/or clinical assessments will also be captured in the appropriate CRF.

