7. Infusion of study drug to be given over 15 (\pm 5) minutes followed by a 30 (\pm 10) minute observation period.
8. Surgical excision occurs 1 to 5 days after the panitumumab-IRDye800 infusion based on subject availability/scheduling.
9. Tumors will be imaged intraoperatively using the devices listed in Appendix B to determine threshold of detection.
10. All resected tissues will be evaluated for near-infrared fluorescence (NIR) fluorescence prior to and after pathological examination.
11. Serum pregnancy test will be obtained on all women of childbearing age at screening; a urine pregnancy test will be performed on Day 0 if the result of a serum pregnancy test within 72 hours before administration of panitumumab-IRDye800 is not available.
12. Blood will also be obtained as needed to evaluate any abnormal lab values experienced after study drug infusion. Blood will not be taken at Day of Discharge if it is within the window of their Day 15 visit.
13. Lymphoseek will be administered locally on the day before surgery. Directly after injection, lymphoscintigraphy will be performed to identify the drainage pattern of the tracer and to identify hot spots (ie, sentinel nodes). SPECT/CT imaging will be performed to determine the anatomical location of the hot spots.
14. Concurrent medications will be reported at screening, Day 0 and Day 15, and in-between if any medication is given to treat adverse events or serious adverse events that in the assessment of the PI are possibly, probably or definitely related to a study procedure.
15. See Section 7.5.1 for adverse events monitoring and reporting.

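### The Section 7.5.1 exemption for early SAEs runs past the Day 0 infusion, and Section 7.5.2 requires those same SAEs to be reported

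*Combined protocol and SAP*

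**What the plan says.** Section 7.5.1 sets the collection rule: "All adverse events (AEs), regardless of seriousness or relationship to study drug, are to be collected only on designated study dates", from consent to 30 days after study drug, recorded on study worksheets, with three listed exceptions. The third concerns serious events: "SAEs that occur from signing of informed consent to prior to Day 1 may not be collected unless assessed as possibly", and the condition goes on to probable or definite relation to a study procedure.

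Section 7.5.2 sets the reporting rule. The Protocol Director must send the Sponsor, within 24 hours of learning of it, "any serious adverse event, whether or not considered related to study drug". All grades are included, and the SAE case report form is used. For the higher grades, "SAEs CTCAE Grade 3 and above, and all subsequent follow-up reports will be reported to the Stanford Cancer Institute" DSMC, again regardless of relatedness. Neither sentence has a start day or refers back to the exceptions in 7.5.1.

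The day numbering comes from Section 9. Footnote 5 of Section 9.1 states "Serum level of panitumumab-IRDye800 will be drawn on Day 0 prior to dose", Section 9.2.2 lists the infusion under Day 0, and footnote 8 states "Surgical excision occurs 1 to 5 days after the panitumumab-IRDye800 infusion". For Cohort 1, footnote 13 states "Lymphoseek will be administered locally on the day before surgery".

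**The concern.** An exemption for SAEs before treatment is common and would raise little concern if it closed at dosing. This one closes at Day 1, and dosing is on Day 0. It therefore includes hours in which the subject has already received an unapproved agent and, in some cases, the radiotracer too.

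For an SAE in those hours that is not judged related, two sections of one protocol give different instructions. Under 7.5.1 it need not be collected. Under 7.5.2 it must be reported on a form within a day. The documents do not say which section prevails. At stake is whether the study's own adverse event record agrees with what the Sponsor and the DSMC receive, for events on the dosing day. Recording such events whatever their presumed cause is what allows the causality call to be looked at again later.

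**Working it through.** No published figure is involved, so the check sets the sections side by side.

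**1. Where the exempt window ends.** The infusion is on Day 0 (Section 9.1 footnote 5; Section 9.2.2; also Section 2.4.2.3). Surgery is 1 to 5 days after the infusion and is labelled Day 1 to 5, so days are counted from an infusion on Day 0. No section makes Day 1 the infusion day. A window that closes just before Day 1 therefore includes the infusion, the 30 (±10) minute observation period and the rest of Day 0.

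**2. Whether it reaches Lymphoseek.** With surgery on Day d, Lymphoseek is given on Day d − 1. This is Day 0 only if d = 1. Only Cohort 1 receives it, so at most 10 subjects are affected.

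**3. How a Day 0 SAE after the infusion, not judged related, is handled.**

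| Rule | Treatment |
|---|---|
| 7.5.1, third exception | need not be collected |
| 7.5.2, Sponsor | report within 24 hours, any grade, on the SAE form |
| 7.5.2, DSMC | report if Grade 3 or above, regardless of relatedness |

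The wording of the exception can be read as permission or as prohibition. Either reading conflicts with 7.5.2.

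**4. How a non-serious, non-laboratory Day 0 event is handled.**
- First exception: covers events that are solely laboratory values, so it does not apply.
- Second exception: covers the period after resection. The earliest surgery is Day 1, so it does not apply.
- Third exception: covers SAEs only, so it does not apply.
- The list of expected post-operative events kept only in the health record does not apply before surgery either.

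Such an event must be collected. A serious event on the same day, not judged related, need not be. The protocol gives no reason for this ordering.

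**5. Who passes through the window.** 10 subjects in Cohort 1 + 10 in Cohort 2 = 20 (Table 1). This counts people, not events. The documents give no rate for SAEs not judged related, so no expected number of missing records follows.

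**The case against.** The strongest reply is that little is lost. Section 7.5.2 is mandatory and itself creates a study record on the SAE form, source notation is required, and SAEs are tracked to resolution or for 30 days after the last dose. A site that follows 7.5.2 documents every Day 0 SAE it knows of. This stands, and it limits the point to a possible gap in the 7.5.1 worksheets. It does not remove the conflict. Calling one section collection and the other reporting does not help, because the report itself needs a form.

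A second reply is that Day 1 was probably meant as the day of first dose. That is plausible, but nothing in the documents says so and all the day numbering points the other way.

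A reader might also infer several stronger things that the documents do not support:

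- **That 7.5.1 contradicts its own opening sentence**, "Both serious and non-serious AEs will be clearly noted in source documentation and listed on study-specific Case Report Forms". That is a general rule, and the section goes on to list exceptions to its collection rule.
- **That the Day 0 adverse event assessment in Section 9.2.2 is a further contradiction.** Footnote 15 to the adverse event row of the calendar refers to 7.5.1, so the calendar defers to it.
- **That infusion reactions would go unrecorded.** The exemption keeps SAEs related to a study procedure, and Sections 9.1 and 9.2 list the infusion and the Lymphoseek injection among the study procedures. A reaction judged related should still be collected. One reservation remains: the term is not defined, Section 7.3 defines causality against study drug only, and the other two exceptions say study drug where this one does not.
- **That the stopping rule is compromised.** A DLT must be judged possibly, probably or definitely related (Sections 2.4.2.2 and 4.4). The count changes only if a causality call is wrong.

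**Conclusion.** The point holds in a narrow form and should be fixed. The 7.5.1 exemption extends past dosing to the end of Day 0, conflicts with the unqualified duty in 7.5.2, and is looser for serious than for non-serious, non-laboratory events on that day. What may be missing is the worksheet record of SAEs after the infusion on Day 0 that are not judged related. The window applies to all 20 planned subjects and includes the Lymphoseek injection for up to 10 of them, if they have surgery on Day 1.

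The conclusion rests on Day 0 being the infusion day, which Sections 2.4.2.3, 9.1 and 9.2.2 support. The limit on its size rests on two assumptions: that the infusion counts as a study procedure, as the Section 9 headings suggest, and that causality is judged correctly. This is an inconsistency in recording rules. It is not evidence that reports to the Sponsor or the DSMC will fail.

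**What to change.** Make four changes, all in Section 7.5.1:

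1. End the third exception at the start of the Day 0 infusion instead of at Day 1.
2. Word its condition so that an SAE is kept if possibly, probably or definitely related to study drug or to a study procedure.
3. Add that SAEs from the start of the infusion onward are recorded whatever their causality.
4. Add that the remaining exemption, from consent to infusion, does not waive reporting under Section 7.5.2. Without this, the same mismatch would persist for SAEs before the infusion.

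Section 7.5.2 stays as it is. The cost is one edited sentence, two short added sentences and at most a few more SAE forms. Dosing, visits and patient care are unaffected.
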